## 2.2 Secondary Objectives

- To evaluate safety and tolerability of the long-term administration of leuprolide in healthy female volunteers.

## 3. Study Design

### 3.1 General Design

This study will evaluate the safety, PK profile and PD effects of the three Ovarest™ dosing regimens: Leuprolide Oral Tablet, 4 mg, administered qd for 28 consecutive days (Treatment “A”), Leuprolide Oral Tablet, 4 mg, administered bid for 28 consecutive days (Treatment “B”), and Leuprolide Oral Tablet, 10 mg, administered bid for 28 consecutive days (Treatment “D”), in comparison to leuprolide acetate administered IM, Lupron Depot® 3.75 mg (Treatment “C”).

This study was originally designed as a randomized, open-label, parallel-group active-control trial. Up to thirty-two (32) subjects (12 subjects in each Ovarest™ treatment group and 8 subjects in the Lupron Depot group) were planned to be randomly assigned to the study drug in a A:B:C ratio of 3:3:2. The randomization schedule was to be balanced by using permuted blocks.

Twenty-three subjects were initially enrolled in this study (9 subjects in each of Ovarest™ treatment groups and 5 subjects in the Lupron Depot group). At the time of the current protocol Amendment, all initially enrolled subjects had completed the study, except for one subject who was withdrawn on post-dose Day 1 (due to vomiting). After interim PK and safety evaluations, it was decided not to enroll any new subjects in Treatment Groups “A”, “B” and “C”. Instead, up

[figure not shown]
to twelve (12) subjects will be enrolled in a new Treatment Group “D” (Leuprolide Oral Tablet, Ovarest™, 10 mg, administered twice daily (bid), 12 hours apart for 28 consecutive days).

Subjects assigned to the third Ovarest™ dose (Treatment “D”) had study drug administered in the same fashion as Treatment “B”. Assessments of the PD profile of treatment “D” had to mimic evaluations of Treatment “B”. However, unlike other Ovarest™ groups, Treatment “D” does not have comprehensive assessments of the PK profile. The subjects that have already participated in this study could be invited to receive Treatment “D” if they were eligible per the study inclusion and exclusion criteria.

The study consists of two major periods: approximately one month of dosing (either 28 consecutive days of daily oral dosing, or a single IM injection on Treatment Day 1) and approximately 1 month (28 days) of post-dosing PK/PD evaluations. The total study duration from screening to the final study visit will be up to approximately 3.5 months.

Study design schematic is displayed in Figure 1 below.

**Figure 1 Study Design Schematic**

### 3.2 Study Procedures

The overall schedule of procedures and assessments is provided in the protocol.

### 3.3 Treatment Description

The treatments administered in this study are presented in [Table 3-1](#).

**Table 3-1 Treatment Description**

Treatment	Description
A	Leuprolide Oral Tablet, Ovarest™ 4 mg, administered qd for 28 consecutive days
B	Leuprolide Oral Tablet, Ovarest™ 4 mg, administered bid for 28 consecutive days
C	Leuprolide Acetate IM, Lupron Depot® 3.75 mg, administered for one month of therapy
D	Leuprolide Oral Tablet, Ovarest™ 10 mg, administered bid for 28 consecutive days

Subjects meeting the eligibility criteria were to be initially randomized to receive one of the two doses of Ovarest™ for 28 days or a monthly IM dose of Lupron Depot®. After the protocol amendment, subjects meeting the eligibility criteria were to be enrolled in Treatment “D” The initially randomized subjects had to start dosing (Treatment Day 1) on either days 1-4 or days 18-28 of their menstrual cycle. Subjects enrolled to the third oral dose (Treatment “D”) had to start dosing 5-9 days before the anticipated start of their next menstrual cycle, based on their self-reported menstrual cycle length and the day the current menstrual cycle began.

### 3.4 Subject Withdrawal and Replacement

Every subject has the right to refuse further participation in the study at any time and without providing reasons for this decision and without prejudice to further treatment. A subject’s participation is to be terminated immediately upon their request.

The subject may be withdrawn from the study at any time at the discretion of the Investigator. Should the subject, during the course of the study, develop conditions that would prevent the subject from being dosed as per Investigator’s judgment (e.g., absolute contraindications, prohibited concomitant medications) or would be considered as potentially dangerous AEs, they must be withdrawn immediately.

A positive alcohol breath test, urine drug screen, or cotinine test will also be grounds for subject withdrawal. If pregnancy occurs or is suspected during study drug treatment, the subject must be discontinued immediately.

The termination of an individual's participation should be considered in case of a serious adverse event (SAE) or considerable worsening of the subject's clinical conditions.

At the discretion of Enteris BioPharma, the entire study or part of the study may be canceled for medical or other reasons. In case of premature termination or suspension of the study or part of the study, the Sponsor will promptly inform the Investigator/institutions, regulatory authorities and IRBs of the termination or suspension and the reason for the measure.

In addition, Enteris BioPharma retains the right to end the study at any time if the study cannot be carried out as agreed upon in the protocol.

The reasons for discontinuation include:

- AE
- Death
- Pregnancy
- Protocol violation
- Lost to follow-up
- Study terminated by Sponsor
- Noncompliance with study drug (to be handled on a case-by-case basis)
- Withdrawal by subject decision (appropriate details must be provided on the CRF)
- Physician decision (appropriate details must be provided on the CRF)
- Other

Subjects discontinued early after having received at least one dose of study drug will not be replaced. Study drug assigned to the withdrawn subject may not be given to another subject.

Data generated from screening failures (subjects not admitted to the study after the screening phase and not assigned a randomization number) may be listed according to main reason for not being admitted into the treatment phase.

#### **4. Changes from the Protocol**

Any changes in planned analyses compared to the protocol will be noted in this section.

Primary statistical analyses of the PD endpoints will utilize measurements for Treatment Day 22 and Treatment Day 29 (not Treatment Day 28 as noted in the protocol). This change will ensure consistent methodology across all treatment groups some of which (Treatments "C" and "D") did not have scheduled PD assessments on Treatment Day 28.

Suppression of  $E_2 \leq 50$  pg/mL,  $\leq 60$  pg/mL, and  $\leq 70$  pg/mL may also be assessed, if considered necessary.

The determination of the suppression of  $E_2$  or other PD endpoints across evaluation intervals was clarified.

An additional analysis for the adverse drug reactions (ADR) (excluding the PT “Menstrual Disorder”) was described.

## 5. Primary and Secondary Parameters

### Primary Parameters

- Comparative evaluation of safety and tolerability variables, by treatments (refer to Section 9).
- PK parameters as  $C_{max}$ ,  $T_{max}$ ,  $AUC_{0-24}$ ,  $AUC_{0-t}$ ,  $AUC_{0-inf}$ ,  $C_{ss\_oral}$ ,  $C_{ss\_im}$ ,  $K_{el}$ ,  $K_{el\ Lower}$ ,  $K_{el\ Upper}$ , and  $T_{1/2el}$  for leuprolide (refer to Section 10).
- PD parameters derived from LH, FSH,  $E_2$ , and Progesterone levels (refer to Section 11).

### Secondary Parameters

- Safety and tolerability variables for long-term administration of leuprolide in healthy female volunteers (refer to Section 9)

## 6. Analysis Populations

### 6.1 Safety Population

All subjects who received at least one dose of study medication will be included in the safety population. Subjects will be analyzed based on the actual treatment received.

In addition to the overall safety population, separate safety populations will be identified for the two study subperiods (a 28-day dosing cycle and a 28-day postdosing evaluation period).

The subjects in Treatment “D” that have already participated in this study (have received Treatments “A”, “B”, or “C”), will be considered in all listings and summaries as completely new study participants with subject identifiers for the study (SUBJID) unrelated to their previous numbers. Unless otherwise noted, these subjects will not be flagged as previous study participants in any statistical summaries and/or individual data listings.

### 6.2 Pharmacokinetic Populations

#### 6.2.1 Primary PK Population

The primary PK population is defined as the group of randomized subjects who completed 28 days of dosing without major protocol violations and for whom the PK profile can be adequately

characterized. For Treatment “D”, primary PK population is defined as a population of subjects who completed 28 days of dosing without major protocol violations.

### **6.2.2 Supportive PK Population**

The supporting PK population is defined as the group of randomized subjects who received at least one dose of study medication and provided any PK data.

Here are some aspects to be considered (but not to be limited to) when determining subject eligibility for PK population: inclusion and exclusion criteria, acceptable times for visit dates and measurements, compliance with treatment, the nature and quality of the data, withdrawal and any protocol deviation. The final responsibility of deciding which subjects are to be included or excluded lies with the principal investigator and the sponsor.

In addition to the overall PK population, separate PK populations will be identified for the two study subperiods (a 28-day dosing cycle and a 28-day postdosing evaluation period).

## **6.3 Pharmacodynamic Populations**

### **6.3.1 Primary PD Population**

The primary PD population is defined as the group of randomized subjects who completed 28 days of dosing without major protocol violation.

### **6.3.2 Supportive PD Population**

The supporting PD population is defined as the group of randomized subjects who received at least one dose of study medication and provided any PD data.

In addition to the overall PD population, separate PD populations will be identified for the two study subperiods (a 28-day dosing cycle and a 28-day postdosing evaluation period).

## **7. Interim Analyses**

No formal interim analysis was planned.

However, there was a preliminary evaluation of the PK and PD results for administrative purposes. The results of the preliminary evaluations triggered a protocol amendment and an introduction of Treatment “D”. See section 3.1 for additional details.

## **8. Study Population and Exposure**

Shells for all summary descriptive statistic tables, figures and listings referred to in this section are displayed in separate mock shells document. The shells may be revised as they are presented

to illustrate the general layout of data to be included in the final report. No inferential analyses are planned. No data imputation methods will be utilized i.e. only observed data will be used.

### **8.1 Subject Disposition**

Subject disposition will be summarized by treatment group (frequency and the percentage of subjects). The reason for discontinuation will be also listed.

The subject disposition summaries will be presented for the entire study and separately for the two study subperiods (a 28-day dosing cycle and a 28-day postdosing evaluation period).

### **8.2 Protocol Deviations**

The protocol deviations will be listed by subject. The protocol deviation criteria have to be endorsed by the sponsor prior to the database lock.

### **8.3 Demographics and Baseline Characteristics**

The descriptive statistics (mean, median, standard deviation [SD], minimum [Min], maximum [Max], and sample size as n) will be reported for continuous variables (age, body mass index [BMI], height, and weight). Frequency counts and percentages will be tabulated for categorical variables (age group, gender, ethnicity, and race). Results will be presented by treatment group. All demographic and baseline characteristics will be listed by subject.

### **8.4 Medical History**

Medical history records will be listed by subject. The Medical Dictionary for Regulatory Activities (MedDRA®) Version 20.1 will be used to classify all medical history findings by System Organ Class (SOC) and Preferred Term (PT).

### **8.5 Prior and Concomitant Medications**

The use of concomitant medications will be monitored throughout the study. The World Health Organization Drug Dictionary (WHO DD) Version Sep2017, format B will be used to classify all medication reported before and during the study.

The prior and concomitant medication summaries will be presented for the entire study and separately for the two study subperiods (a 28-day dosing cycle and a 28-day postdosing evaluation period).

Prior and concomitant medications (with a study subperiod noted) will be listed by subject.

### **8.6 Study Drug Administration**

The study drug administration details (including duration of dosing period, compliance with the dosing regimen, etc.) will be summarized by treatment group. The compliance rates will be

evaluated for the Ovarest™ groups only as a percentage of days with the protocol-specified dosing during the scheduled 28-dosing interval.

The study drug administration details (including treatment or dose received, date and time of administration, number of pills administered daily, and compliance with the fasting requirements) will be listed by subject.

## **9. Safety Analyses**

Safety data evaluations will be based on adverse events (AEs), laboratory test results, clinical signs and symptoms from physical and gynecological examinations, electrocardiogram (ECG) and vital signs assessments.

Safety parameters will be summarized by treatment group for the entire study and separately for the two study subperiods (a 28-day dosing cycle and a 28-day postdosing evaluation period).

Shells for all summary descriptive statistic tables and listing referred to in this section are displayed in the document containing the TFL shells; the shells may be revised as they are presented to illustrate the general layout of data to be included in the final report.

### **9.1 Physical Examination Findings**

Physical examinations and gynecological examinations will be performed at screening, end of dosing period (Post-dosing Day 1) and at the Final Visit and also in case of early discontinuation

Any abnormal findings judged to be clinically significant prior to first dose will be documented as medical history and those after first dose will be captured as an AE (treatment emergent AE; [TEAE). Any physical or gynecological examination findings documented as AEs will be included in the AE summaries (overall summaries and summaries for study subperiods).

### **9.2 Adverse Events**

Treatment-emergent AEs (TEAEs) and non-TEAEs (those occurring prior to administration of study medication or those first occurred prior to study drug administration and did not worsen in frequency or severity) will be listed. TEAEs will be defined as AEs that occur on or after the date and time of study drug administration, or those that first occur pre-dose but worsen in frequency or severity after study drug administration. TEAEs will be captured through the end of the entire study including two study sub-periods (a 28-day dosing cycle and a 28-day post-dosing evaluation period) or which occur within 30 days following the final examination. In addition, TEAEs with a start date and time during a particular study sub-period will be attributed to the corresponding subperiod.

Serious adverse events (SAEs), which occur during this study or within 30 days following the final examination, will also be listed separately and described in the study report.

The incidence of TEAEs will be summarized for entire study and separately for the two study sub-periods (a 28-day dosing cycle and a 28-day post-dosing evaluation period) using the safety populations for any particular study subperiods. The MedDRA® dictionary Version 20.1 will be used to classify all TEAEs reported during the study by SOC and PT.

Incidence of subjects who experienced TEAEs will be presented by treatment group, by SOC, PT, by investigator-assessed causality (relationship to study drug) and severity. Each subject may only contribute once to each of the incidence rates, for a TEAE following a given treatment, regardless of the number of occurrences; the highest severity or highest causality will be presented, as appropriate. In each summary table, SOC will be presented in descending order of overall incidence rate in terms of frequency of subjects and then in frequency of events (alphabetical order will be used in case of equal rates). For each SOC, PT will be presented the same way. Incidence of TEAEs (number of events) will also be presented by treatment, SOC, and PT, by investigator-assessed causality and severity.

The causality of TEAEs will be classified according to the study protocol as Unrelated, Possibly Related, Probably Related, or Definitely Related. The severity of TEAEs will be rated as per the protocol as mild, moderate, or severe.

Adverse drug reactions (ADR) are defined in the ICH Guidance for Industry E2A: clinical safety data management: definitions and standards for expedited reporting as follows: “All noxious and unintended responses to a medicinal product related to any dose should be considered adverse drug reactions (ADR).” An ADR can therefore be any TEAE judged related to the medicinal product (causal relationship between a medicinal product and an AE is at least a reasonable possibility, i.e., the relationship cannot be ruled out).

In accordance with the prescribing information for Lupron Depot and other amenorrhea-inducing drugs, one category of ADR (represented by the PT “Menstrual Disorder”), may be analyzed as both TEAE and a metric of the menstrual bleeding pattern (e.g., a number of bleeding days during the dosing interval).

As an additional ADR analysis, incidence of subjects who experienced ADR will be presented by treatment group, by SOC, and PT, excluding the PT “Menstrual Disorder”.

The incidence of ADRs will be summarized for entire study and separately for the two study sub-periods (a 28-day dosing cycle and a 28-day post-dosing evaluation period) using the safety populations for any particular study subperiods. Each subject may only contribute once to each of the incidence rates, for an ADR following a given treatment, regardless of the number of occurrences. In summary table, SOC will be presented in descending order of overall incidence rate in terms of frequency of subjects and then in frequency of events (alphabetical order will be used in case of equal rates). For each SOC, PT will be presented the same way. Incidence of ADR (number of events) will also be presented by treatment, SOC, and PT.

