After the 28-day dosing period, four follow-up visits will be scheduled at 7, 14, 21, and 28 days after the last dose. During each follow-up visit, blood samples will be drawn to assess leuprolide (via a single blood draw) and LH, FSH, E2, and progesterone concentrations. During each follow-up visit, subjects will be asked about onset (or absence) of menstrual period.

Safety laboratory evaluations will also be performed during the 28-day postdosing visit. The 28-day postdosing visit will be considered the Final Study Visit. In addition to the PK/PD and safety laboratory assessments, ECG, physical and gynecological examinations will also be performed.

A total of 55 PK blood samples will be taken from subjects in the oral groups (Treatments “A”, and “B”) for the evaluation of the leuprolide serum concentrations. A total of 11 PD blood samples will also be taken for the determination of LH, FSH, E2, and progesterone levels. The blood volume for each PK sample is assumed to be approximately 3 mL for leuprolide analysis, and the volume for each PD sample is assumed to be approximately 16 mL (10 mL for progesterone and estradiol analysis, and 6 mL for FSH and LH analysis). The total amount of blood volume for all PK and PD draws is 341 mL. Four safety blood draws will be performed during the study with a volume of 8 mL per draw. An

additional 34 mL of blood may be drawn during the study to allow for repeat draws and/or additional safety tests and for the screening pregnancy test. The total amount of blood drawn should not exceed 407 mL over 3 months, including all samples collected for PK and PD analyses and eligibility and safety purposes.

In the Treatment group “D” the total number of samples for PK evaluations will be reduced by 46 when compared to other oral groups. The total amount of blood drawn will be reduced by 138 mL (46 x 3 mL) and should not exceed 269 mL over 3 months, including all samples collected for PK and PD analyses and eligibility and safety purposes.

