### 11.1 Definition of Adverse Events

AEs or adverse experiences are defined in the (ICH) Guidance for Industry E6: Good Clinical Practice as follows:

An AE is any untoward medical occurrence in a patient or clinical investigation subject administered a pharmaceutical product and that does not necessarily have a causal relationship with this treatment. An AE can therefore be any unfavorable and unintended sign (including an abnormal laboratory finding), symptom, or disease temporally associated with the use of a medicinal (investigational) product, whether or not related to the medicinal (investigational) product (ICH April 1996).

Any medical condition or clinically significant laboratory abnormality with an onset date before the first date of study drug administration is considered to be preexisting, and should be documented in the CRF.

Any AE (*ie*, a new event or an exacerbation of a preexisting condition) with an onset date after study drug administration up to the last day on study (including the follow-up, off-study medication period of the study), should be recorded as an AE on the appropriate CRF page(s) (see Section 11.2 for details).

An AE does not include:

- Medical or surgical procedures (*eg*, surgery, endoscopy, tooth extraction, transfusion); the condition leading to the procedure is an AE
- Preexisting diseases or conditions present or detected prior to start of study drug administration if they do not worsen
- Situations where an untoward medical occurrence has not occurred (*eg*, hospitalization for elective surgery, social and/or convenience admissions)

- Overdose of either study drug or concomitant medication without any signs or symptoms unless the patient is hospitalized for observation

The period of observation for AEs starts at first dose of study drug and continues until the subject undergoes a final examination as part of the study. The period will also include 30 days following the final examination during which time SAEs must be reported. AEs occurring after the completion of the study must be reported if the Investigator considers that there is a causal relationship with the study medication.

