### 11.3 Reporting of Serious Adverse Drug Experiences, Including Deaths

A serious adverse drug experience (SAE), as defined in 21 CFR 312.32 is:

Any adverse drug experience occurring at any dose that results in any of the following outcomes:

- Death
- A life threatening adverse drug experience
- Inpatient hospitalization or prolongation of existing hospitalization
- A persistent or significant disability/incapacity
- Congenital anomaly/birth defect

Important medical events that may not result in death, be life-threatening, or require hospitalization may be considered a serious adverse drug experience when, based upon appropriate medical judgment, they may jeopardize the patient or subject and may require medical or surgical intervention to prevent one of the outcomes listed in this definition. Examples of such medical events include allergic bronchospasm requiring intensive treatment in an emergency room or at home, blood dyscrasia or convulsions that do not result in inpatient hospitalization, or the development of drug dependency or drug abuse.

Serious adverse experiences, including death due to any cause, which occur during this study or within 30 days following the final examination, whether or not related to the administration of study drug, must be reported immediately (within 24 hours of learning of the event) to the Medical Monitor.

Contact:	[name]
[contact]
Back up [contact]
[contact]

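### SAP 9.2 counts TEAEs for 30 days after the final examination, a period in which the protocol collects only serious or investigator-judged related events

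*SAP*

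**What the plan says.** **Collection (protocol).** Section 11.1 sets the main window: "The period of observation for AEs starts at first dose of study drug and continues until the subject undergoes a final examination". Within it every new or worsened event counts, serious or not: an event with onset "up to the last day on study (including the follow-up, off-study medication period of the study), should be recorded as an AE". After the final examination the duty narrows. For serious events: "The period will also include 30 days following the final examination during which time SAEs must be reported". For the rest: "AEs occurring after the completion of the study must be reported if the Investigator considers that there is a causal relationship". Section 11.3 repeats the SAE rule for events "which occur during this study or within 30 days following the final examination, whether or not related to the administration of study drug". Section 7.1 fixes the end point for a completer: "The 28-day postdosing visit will be considered the Final Study Visit".

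**Counting (SAP).** Section 9.2 captures TEAEs through the dosing and postdosing subperiods "or which occur within 30 days following the final examination". Nothing restricts that last part to serious or related events. Allocation to subperiods is by onset: "TEAEs with a start date and time during a particular study sub-period will be attributed to the corresponding subperiod". TEAE incidence is then tabulated for the whole study and for each subperiod, by SOC, PT, causality and severity, both as subjects and as numbers of events. An adverse drug reaction (ADR) is any TEAE judged related, and it gets its own table over the same periods.

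**Elsewhere in the SAP.** Sections 9.3 and 9.4 end the whole-study analyses of laboratory results, vital signs and body weight at the final visit. Section 4, which records departures from the protocol's planned analyses, does not mention the TEAE window.

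**The concern.** The counting window is longer than the window in which all events are collected. A non-serious event judged unrelated counts if it starts before the final visit. If it starts the week after, nobody is required to report it. A related event is reportable in both weeks. If both stretches feed one table, the causality breakdown describes a mixture of two collection rules.

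The second issue is reconciliation. The second subperiod ends at the final visit, so an event in the next 30 days could appear in the overall table and in neither subperiod table. The label for the whole study would also mean one window for adverse events and another for laboratory and vital-sign data within the same SAP section.

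The stake is modest. These are descriptive tables, but Protocol 12.5 expects the safety assessments to support dose selection in later studies, and the arms are small enough for single subjects to show.

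**Working it through.** The plan states no figure on this point, so there is none to reproduce. The check compares the windows and then illustrates the possible size.

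**1. Windows for a completer** (Protocol 7.1 and 11.1; SAP 9.2)

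| Stretch | Days | Protocol collects | TEAE under SAP 9.2 | Subperiod |
|---|---|---|---|---|
| Dosing cycle | 28 | all AEs | yes | first |
| Postdosing period | 28 | all AEs | yes | second |
| After final examination | 30 | SAEs; other AEs only if judged related | yes | none |

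The TEAE window is 28 + 28 + 30 = 86 days, of which 30/86 = 34.9% is under selective collection. This is a share of calendar time, not of events.

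**2. Effect on the related share of events.** Two assumptions are needed, because the documents give no event rates. Let f be the related fraction over the 56 study days. Let r be the rate of related events in the last 30 days relative to the rate during the study. Assume all related late events are reported, and ignore unrelated late SAEs, which would pull the other way. Then

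related share = (56f + 30fr) / (56 + 30fr)

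overall events / sum of subperiod events = (56 + 30fr) / 56

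For f = 0.4:

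| r | 30fr | Related share | Overall / sum of subperiods |
|---|---|---|---|
| 0 | 0 | 22.4/56 = 40.0% | 1.000 |
| 0.1 | 1.2 | 23.6/57.2 = 41.3% | 1.021 |
| 0.25 | 3 | 25.4/59 = 43.1% | 1.054 |
| 0.5 | 6 | 28.4/62 = 45.8% | 1.107 |
| 1 | 12 | 34.4/68 = 50.6% | 1.214 |

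For f from 0.2 to 0.6 and r from 0 to 1, the share rises by 0 to about 11 points and the ratio runs from 1.000 to 1.321.

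**3. Where r is likely to lie.** In the oral arms the last 30 days are days 29 to 58 after the last dose. The label in Protocol Appendix D gives a terminal half-life of about 3 hours after an intravenous dose, so values of r near 1 are implausible. The same label says normal function usually returns within three months of stopping the depot, so r = 0 is not assured either.

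**4. Weight of one subject.** The step 2 figures apply to event counts. In the subject tables each subject counts once per row, so a late event matters only if the subject is new to that row or moves to a higher causality class. One additional subject adds 1/9 = 11.1 points in A or B, 1/5 = 20.0 points in C, and 1/12 = 8.3 points in D if 12 enrol (arm sizes from Protocol 7.1).

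**5. With the window closed at the final examination.** The window is 28 + 28 = 56 days, all under full collection. Every event starting after first dose falls in one subperiod, and the event-count ratio is 1.000.

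**The case against.** The strongest reply is that the SAP never says outright that late events enter the whole-study table. Its sentence sets the 30 days apart from the study with an *or*, the SAE sentence makes the same split, and sections 9.3 and 9.4 close the whole study at the final visit. On that reading late TEAEs are defined and perhaps listed but not tabulated, and there is neither tilt nor mismatch. The SAP could also be said to follow Protocol 11.1, which itself extends the observation period by 30 days.

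Part of this stands: the point rests on the natural reading, not on an explicit instruction. But the SAP defines these events as TEAEs, says TEAEs will be tabulated, and has no rule leaving them out. Protocol 11.1 extends the period for SAEs, not for all events. If exclusion was intended, the sentence still needs to say so.

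A reader might infer more than the documents support:

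- *That the ADR table is tilted toward related events.* It holds only related events by definition, and the protocol asks for related events after study completion as well. Its window is longer; its composition is not selected on relatedness.
- *That severity grades shift.* Serious is not the same as severe. The tables use mild, moderate and severe, and no shift in these is shown.
- *That the subject tables ought to add up.* They never do, because one subject can count in both subperiods. Pre-dose events that worsen may also lack a subperiod by start date. The loss of match concerns event counts and the set of subjects covered.
- *That the distortion is large.* With f = 0.5 and r = 1 the related share would read (28 + 15)/(56 + 15) = 61%. That needs an undiminished rate of related events 29 to 58 days after the last oral dose, and it applies to event counts only.

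**Conclusion.** The mismatch between what is collected and what is counted is in the text. On the natural reading, the whole-study TEAE tables mix two collection rules, the related share in the causality breakdown can rise, and overall event counts can exceed the two subperiod counts combined. This assumes that late events are tabulated and that they are more often related than events during the study.

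The size is not derivable from the documents. It is nil without late events and probably small, with the caveat that one additional subject is worth 8 to 20 percentage points. The collection rule is identical across arms, so the rule itself creates no between-arm bias. Open-label causality judgement affects every event in this study, not just the late ones. SAP section 8 plans no inferential analyses, so no error rate is involved. This is a low-cost improvement to the SAP, not a threat to the trial's conclusions.

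**What to change.** In SAP 9.2, end the TEAE incidence tables at each subject's final examination (Postdosing Day 28, or the early discontinuation visit). This matches the whole-study window in sections 9.3 and 9.4. List SAEs and related AEs from the following 30 days separately; a separate SAE listing is already planned.

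For the ADR table, either apply the same cut-off so that both tables share one window, or keep the late ADRs there with a flag. The selection argument does not require removing them, so this is a matter of consistency.

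The cost is one sentence in the SAP and a date cut-off in the programs. No new data are needed and no reported event is lost. The downside is that late related events appear in a listing rather than in the incidence table.
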